6.2 Anticipated Risks

All patients will be exposed to the potential risks associated with all medical procedures (including death). Potential adverse events include the following:

1. The general complications of any colorectal surgery.
 - a) Pelvic complications
 - i. Anastomotic bleeding
 - ii. Anastomotic stricture
 - iii. Anastomotic fistula
 - iv. Anastomotic leakage
 - v. Anastomosis dehiscence
 - vi. Pelvic abscess, collection
 - vii. Colonic ischemia
 - viii. Peritonitis
 - b) Ileus
 - c) Small bowel obstruction
 - d) Incisional hernia
 - e) Bleeding
 - f) Organ injury (e.g., bladder, bowel, ureter)
 - g) Nerve tissue injury
 - h) Surgical Site Infection
 - i) Prolapse
 - j) Acute renal failure
 - k) Sepsis
 - l) AEs associated with potential stoma placement/stoma reversal
 - m) Death
2. Adverse events that may probably be caused by or associated with the use of the Colovac 2 Device (during and after implant period) include:
 - a) Complications from device malfunction that lead to early removal of device and stoma conversion (e.g., migration, stent collapse) such as:
 - i. Pelvic complications (abscess, collection)
 - ii. Anastomosis complications (leakage, fistula, dehiscence)
 - iii. Peritonitis
 - iv. Sepsis
 - v. Colon perforation, obturation or occlusion
 - vi. AEs associated with stoma conversion procedure
 - b) Ileus
 - c) Small bowel obstruction
 - d) Colonic ischemia
 - e) Colonic stenosis
 - f) Colon wall damage (e.g., inflammation, hyperplasia, fibrosis, edema, erosion, ulceration)
 - g) Abdominal/Anal pain
 - h) Temporary feces and gas incontinence

SAFE-2023 Colovac 2 Study Clinical Investigation Plan

-
- i) Diarrhea or constipation
 - j) Inflammation of skin around the anus
 - k) Prolapse
 - l) Complication associated with an attempt to reposition the Colovac 2 Device (although Warnings instruct not to re position the Colovac Device)
 - m) Complication associated with having to remove the Colovac 2 Device surgically – if endoscopic retrieval is impossible
 - n) Adjacent organ injury due to a broken stent wire poking through the colon
 - o) Additional complications reported for other colorectal stents:
 - i. Tenesmus
 - ii. Fecal impaction
 - iii. Bacteremia/fevers
 - iv. Foreign body sensation
 - v. Intestinal colic (pain not related to operative site)
 - vi. Bleeding/blood from anus
 - vii. Nausea
 - viii. Inability to eat
 - ix. Cramping
3. Medication side effects, especially anesthesia reactions, including:
- 1) Respiratory insufficiencies
 - 2) Sedation-induced apnea
 - 3) Pneumonia
 - 4) Hypotension
 - 5) Cardiac arrest (death)
 - 6) Nausea and/or vomiting
4. Adverse events associated with the stoma:
- 1) Skin complications
 - a) Peristomal dermatitis
 - b) Skin irritation
 - c) Skin breakdown
 - 2) Parastomal ulceration
 - 3) Parastomal hernia
 - 4) Stoma complications:
 - a) Stoma necrosis
 - b) Stoma retraction
 - c) Stoma prolapse
 - d) Stoma stenosis
 - 5) Dehydration
 - 6) Intestinal Obstruction
 - 7) Infection
 - 8) Sepsis
5. Adverse events associated with stoma reversal:

**SAFE-2023 Colovac 2 Study
Clinical Investigation Plan**

- 1) Leakage (at the stoma closure site)
- 2) Surgical Site Infection
- 3) Hernia at stoma site
- 4) Small bowel obstruction
- 5) Ileus (no return of bowel function in 7 days per NSQIP definition)
- 6) Renal failure
- 7) Infection
- 8) Sepsis
- 9) Complications that prevent stoma-closure by 12 Months

A discussion of the above-mentioned potential adverse events is available in Section 7.2.1 of the Investigator Brochure.

The anticipated risks for the Colovac device will be updated based on the results of this study. The Colovac risks include the risk of a longer hospital stay (up to 10 days, or longer if an ostomy is required).

6.3 Risk to Benefit Rationale

Based on clinical study results of previous versions of the Colovac device, the benefits of the device outweigh the risks. The anticipated risks for the Colovac 2 device will be updated based on the results of this study and a new benefit-risk assessment for the Colovac 2 device will be performed.

7.0 Investigational Device

The Colovac 2 Colorectal Anastomosis Protection Device Instructions For Use are available in Appendix 1.

The Colovac 2 Colorectal Anastomosis Protection System (Colovac 2 System) consists of the Colovac 2 Colorectal Anastomosis Protection Device (Colovac 2 Device) and the Vacuum Management Device (Smartvac). The Colovac 2 Colorectal Anastomosis Protection Device includes the Colovac 2 Implant and the Colovac 2 Introducer (Table 1).

The Colovac 2 Implant is composed of a stent and sheath, and is designed to be used in conjunction with the SafeHeal Smartvac System including canisters with tubing sets.

The Colovac 2 Colorectal Anastomosis Protection Device is a short-term invasive device delivered and positioned through a natural orifice.

Note that Colovac 2 and Colovac may be used interchangeably for the device, implant, introducer, and system.

Table 1: Components of the Colovac 2 System

Component	Part Number
-----------	-------------

SAFE-2023 Colovac 2 Study Clinical Investigation Plan

Colovac Colorectal Anastomosis Protection Device	040748
Colovac Device	041463
Introducer	035965
SafeHeal Smartvac	40-0016
SafeHeal Canisters with tubing sets	40-0017

The description hereafter is related to the Colovac 2 device the SAFE-2023 clinical trial. It is a clinical device for investigational use. It is a next generation device based on the original Colovac device (FG-02788-CE) that was CE-marked.

The Colovac 2 device is a sterile, single use disposable device.

7.1 Implant

The Colovac 2 Implant (Figure 1- Bottom) is pre-loaded in the Colovac 2 Introducer (Figure 1 - Top).

Note: The Colovac 2 Implant is designed to be used in conjunction with the SafeHeal Vacuum Management Device.

SAFE-2023 Colovac 2 Study Clinical Investigation Plan

[figure not shown]

Figure 1: Introducer pre-loaded with the Colovac Device (Top); Colovac Implant (Bottom)

As shown above in Figure 1- Bottom, the Colovac 2 Implant is composed of:

- An anchor consisting of a covered stent assembly delimiting an air- and water-tight volume (i.e., vacuum chamber) in which a vacuum is pulled through two vacuum tubes once the device is correctly deployed in the colon.
- A flexible cylindrical sheath attached to the anchor, covering the anastomosis and with appropriate length so that it protrudes about five centimeters outside the patient's anus. The sheath is an extrusion with a very thin wall, attached with two sealing rings.

Upon contact with the colonic wall, the sealing rings secure a volume (i.e., vacuum chamber) to which a negative pressure is applied over the vacuum tubes. To provide a vacuum distribution all around the anchor, the surface of the sheath material is outfitted with features to ensure circumferential fluidic communication. As a means for monitoring sheath fluctuation and potential migration, the sheath of the Colovac Implant is printed with marks in 1 cm increments.

SAFE-2023 Colovac 2 Study Clinical Investigation Plan

There are two tubes that pass through the downstream sealing ring and terminate within the vacuum chamber. These tubes supply vacuum to the vacuum chamber.

The upstream ends of the tubes that are within the vacuum chamber are multiperforated. The unperforated section of the tubes pass through the downstream sealing ring and are long enough to protrude outside of the patient's anus and be attached to the SafeHeal Vacuum Management Device by an off-the-shelf barbed connector. The SafeHeal Vacuum Management Device generates negative pressure in the vacuum chamber. The negative pressure draws the colonic wall toward the mesh of the stent and thus anchors the Colovac Device in place and prevents migration. The reduced diameter of the stent within the vacuum chamber is intended to provide additional mechanical engagement within the colon while vacuum is engaged.

7.2 Introducer

The Colovac 2 Introducer (Figure 1 - Top), is a single use device, which is used to deliver the Colovac Device during a colectomy procedure, once the colorectal anastomosis is complete.

The Introducer consists of two coaxial tubes, specifically, the Outer Protection Tube and the Pusher Tube. Both tubes are linked to each other via a handle.

The Outer Protection Tube is a straight tubular external envelope that holds the anchor element (i.e., stent section) of the Colovac 2 Implant in a compressed state during the insertion procedure. Turning the deployment knob clockwise then releases the stent section of the Colovac Implant from the Introducer into the colon (Figure 2). Once the Colovac Implant has been properly placed at the target site, the Introducer is removed from the colon

SAFE-2023 Colovac 2 Study Clinical Investigation Plan

[figure not shown]

Figure 2: Introducer Handle During Placement of Stent (Top -stent completely inside Introducer; Middle – stent partially deployed; Bottom – stent fully deployed)

The Colovac Colorectal Anastomosis Protection Device is packaged in a sterile pouch fitted in a cardboard box together with the Instructions for Use (IFU).

Vacuum Management Device

The Colovac 2 Device is designed to be used in conjunction with the SafeHeal Vacuum Management Device (**Error! Reference source not found. 3**).

SAFE-2023 Colovac 2 Study Clinical Investigation Plan

Figure 3: Vacuum Management Device

The Vacuum Management Device is a single-patient use, non-sterile active device. The device attaches directly to the Colovac 2 Implant and supplies vacuum. It also monitors the vacuum level at the anchoring site, turning on the onboard vacuum pump if the measured vacuum level is outside the pre-determined acceptable range. It provides caregivers with visual and auditory alerts in the event of the following:

- Vacuum Leak detected
- Tubing occlusion detected
- Fluid Collection Cannister full (replacement needed)
- Low Battery (replacement needed)

The housing of the Vacuum Management Device contains several key components, including a vacuum pump (capable of supplying a maximum of -80 kPa), the user interface, the controller printed circuit board, and a battery. The Fluid Collection Cannister interfaces with the housing via a mechanical latching system, creating a seal. An inline filter within the Fluid Collection Cannister protects the vacuum pump. The cannister contains baffling and a fluid absorbent material to absorb any fluids aspirated from the implant. This serves to further protect the vacuum pump.

The vacuum management device is connected to the Colovac device using a tubing set that is supplied with the device.

The System will be indicated for use during patient recovery in hospital/hospital-like environments (e.g., patient hospital rooms).

SAFE-2023 Colovac 2 Study Clinical Investigation Plan

7.3 Mechanism of Action

By means of the Introducer, the stent (i.e., anchor) of the Colovac 2 Device is placed in the gastrointestinal (GI) tract lumen, in the transverse neo-colon above the sacral promontory. The flexible sheath which is attached to the anchoring element extends through the colon, covering the GI wall from the anchoring point down to the rectal pouch or just beyond the anal sphincter, thus fully covering the anastomosis and creating a bypass to keep feces and other from communicating with the anastomosis.

By placing the proximal (downstream) part of the stent in the colon above the sacral promontory, the Colovac Device is securely anchored in an intact section of the colon. Any tension that might be applied to the colonic wall by the Colovac Device due to feces passing through will be absorbed by the intact colonic wall, while the anastomosis will not be affected due to the distance between the stent of the Colovac Device and the anastomosis.

The Introducer consists of two coaxial tubes, specifically, the Outer Protection Tube and the Pusher Tube. Both tubes are linked to each other via a handle.

The Colovac 2 Implant is enclosed within the Outer Protection Tube. The upstream tip of the Introducer holds the stent section of the Colovac 2 Implant. The stent is compressed in a radially retracted position for introduction. When compressed, the Colovac 2 Implant has a reduced diameter (16mm) to enable safe insertion and subsequent deployment into the colon. Once released from the Introducer, the stent will expand radially to its uncompressed state against the colonic wall and will thus secure a volume (Vacuum Chamber). As shown below in Figure 4, the Colovac device is designed with a 26.5 mm central stent portion and 37 mm flare at the end, to provide optimal anchoring in the sigmoid colon, which has an average diameter ranging from 30 – 40 mm¹. Furthermore, the colon diameter adapts to the stent diameter.

The Implant is secured to the colon through the continuous application of a negative pressure, which is generated by the SafeHeal Vacuum Management Device. Vacuum is applied to the Colovac Implant when the ends of the tubes extending from the anus are connected to the tube set attached to the Vacuum Management Device. The resulting negative pressure inside the Vacuum Chamber achieves an anchoring effect by drawing the colon wall to the stent. The controlled anchoring is fully reversible without creating significant damage to the colon. The length of the sheath is such that the sheath covers the anastomosis from the anchoring position to beyond the anal sphincter.,. Refer to the IFU for more details.

The healthy colon tissue in which the Colovac Device is placed has sufficient elasticity to allow colons with smaller diameters to expand without injury to accommodate the device, while the device's negative pressure vacuum pulls colons with larger diameters to the stent wall, allowing the device to anchor securely to the colon.

¹ Atlas of Colonoscopy. Francesco Paolo Rossini, Department of Gastroenterology Ospedale Maggiore Torino Italy.

SAFE-2023 Colovac 2 Study Clinical Investigation Plan

[figure not shown]

Figure 4: Colovac Implant Dimensions

To prevent accidental displacement of the Colovac 2 Implant by accidental pulling on the patient-external section of the vacuum tubes, the external sections of the vacuum tubes may be fixed to the patient's skin by adhesive strips.

8.0 Intended Use

The SafeHeal Colovac 2 Colorectal Anastomosis Protection Device is intended for use in patients requiring low anterior rectal anastomoses to limit stoma creation to only those patients requiring more time for anastomosis healing when the device is removed, allowing patients with a healed anastomosis to avoid stoma creation.

9.0 Study Design

This is a prospective, open-label, single arm study that will enroll up to 50 patients.

9.1 Study Objective:

The objective of the study is to assess the preliminary, safety and performance of the Colovac 2 System.

9.2 Expected date of the clinical investigation initiation

The first subject was enrolled in the clinical study on July 31, 2024.

9.3 Estimated date of the clinical investigation completion

The site is expected to enroll approximately 5 patients each month. Enrollment and follow-up are expected to take approximately 6 weeks to complete per patient.

9.4 Primary Objective

SAFE-2023 Colovac 2 Study Clinical Investigation Plan

The primary study objective is to evaluate the clinically significant (CS) migration rate of the Colovac 2 device during its 10-day implantation period.

9.5 Primary Performance Endpoint at Day 10

The primary performance endpoint is the clinically significant migration rate of the Colovac 2 device during its 10-day implantation period.

Clinically significant migration is defined as movement of device that allows fecal contents to reach the anastomosis site evidenced by:

- Migration of entire stent to or below the Sacral Promontory as indicated by fluctuation in the length of the sheath that extends out of the anus and confirmed by radiographic displacement, with or without subject symptoms or clinical findings suggestive of anastomotic leak (pain, fever, elevated CRP, elevated WBC); or
- Expulsion of the device.

9.6 Secondary Objectives:

The secondary objectives of this study are to assess the:

- Preliminary safety and performance of the Colovac 2 System
- Ease of use of the Colovac 2 Colorectal Anastomosis Protection Device
- Ease of use of the Colovac 2 Introducer and Implant and Vacuum Management Device

9.7 Other Performance Endpoints at Day 10

The other performance endpoints are:

- Ostomy avoidance rate
- Cleanliness of colon immediately prior to device retrieval
- Staff Ease of Use of Device
- Subject Tolerance and Ease of Use of Device

9.8 Safety Endpoints at Day 10

The safety endpoints are:

- Mucosal appearance at anchoring site after device removal
- Device related complications
- All complications

9.9 Measurement Methodology

All patient clinical data will be collected on standardized case report forms.

Safety will be evaluated by determining the incidence of intra- and post-surgical complications and adverse events (including spontaneous patient reports) after 10 days and 4 weeks. Complications and adverse events will be recorded on the case report forms.

SAFE-2023 Colovac 2 Study Clinical Investigation Plan

9.10 Primary Analysis Population

Patients treated with the Colovac 2 Colorectal Anastomosis Protection Device will be included in the intent to treat (ITT) population. Patients who withdraw consent prior to enrollment or who do not meet the eligibility requirements (per the inclusion and exclusion criteria) prior to enrollment will be recorded on a screening log but will not be included in any analyses. Subjects who are enrolled and excluded from the study due to adverse events prior to implantation with the Colovac 2 Colorectal Anastomosis Protection Device will not be included in the ITT population.

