4.3 SAFE-2 Colovac+ Pivotal Study

The SAFE-2 Pivotal IDE Study is a multicenter, randomized, controlled trial comparing the safety and effectiveness of the Colovac+ Colorectal Anastomosis Protection Device (Colovac+) used with the VLAS device to diverting ostomy following low anterior resection. The first two subjects at each site were enrolled in a run-arm and implanted with the Colovac+ device. The other subjects were randomized to either the Colovac+ or Control arm of the study.

A total of 15 Colovac+ subjects were enrolled in the run-in arm of the study, 10 subjects were randomized to the Colovac+ arm, and 8 subjects were randomized to the control arm.

One unanticipated adverse device effect occurred when a surgeon attempted to reposition the device immediately upon completion of insertion of the device (even though the IFU specifically warns against

SAFE-2023 Colovac 2 Study Clinical Investigation Plan

this), followed by his inability to endoscopically remove the device, which necessitated surgical removal of the device. Upon device removal, the subject was safely converted to a stoma. This is the only event of this nature observed in the 27 cases in this IDE study. Additionally, no events of this nature were observed in the European feasibility studies.

The rate of stoma avoidance was 70% in the Colovac+ randomized arm and 53% in the run-in (training) arm. A clean anastomosis was observed in 92% of all subjects in both Colovac+ arms.

No clinically significant device migration occurred but partial migration occurred in 4/14 (28.6%) of the first 15 Colovac+ subjects enrolled. Clinically significant device migration occurred in 3/12 (25.0%) subjects and any migration (includes clinically significant and partial migration) occurred in 6/12 (50.0%) of the last 12 Colovac+ subjects enrolled; however, only 1/12 (8.3%) of these migrations resulted in stoma creation.

As a higher-than-expected migration rate was observed in the last 12 subjects implanted with the Colovac+ device in the study, enrollment in the study was temporarily suspended while a root cause investigation was conducted. The decision to suspend study enrollment was not related to safety concerns with the device or the study.

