 - a) Blood loss (>750 cc)
 - b) Blood transfusion
 - c) Any new sign of ischemia
 - d) Positive air leak test
 - e) Inadequate bowel preparation
 - f) Anastomosis location greater than 15 cm from the anal verge
 - g) Other intra-operative risks that preclude the subject from undergoing the procedure with the investigational device

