10.3 Screening Procedures

All patients considered for colorectal surgery and eligible for enrollment as determined by the study investigator should have the study explained to them, be given the study information sheet and informed consent form, and allowed time to consider whether or not they wish to take part in the study. The Investigator or a member of his/her staff should inform the patient about the study's

SAFE-2023 Colovac 2 Study Clinical Investigation Plan

purpose and risks/benefits. If the patient agrees to take part in the study and signs the consent form, the patient can then be screened by the investigator for study eligibility. If all inclusion criteria and no exclusion criteria are met, the patients should be enrolled in the study. Patients who give consent to take part in the study and subsequently do not meet the eligibility criteria will not be included in the intention to treat (ITT) population as detailed in 8.1.

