16.1.2 Reports

The principal investigator shall report all adverse events and device deficiencies in the appropriate sections of the e-CRF and provide where requested by the sponsor, the necessary clinical or technical information that may contribute to clarifying the circumstances.

The principal investigator shall report:

- a) any serious adverse event (SAE) that has a causal relationship with the investigational device, or the investigation procedure or where such causal relationship is reasonably possible.
- b) any device deficiency (DD) that might have led to a serious adverse event if appropriate action had not been taken, intervention had not occurred, or circumstances had been less fortunate.
- c) any new findings in relation to any event referred to in points a) and b).

to the sponsor immediately, but not later than 3 calendar days after investigation site study personnel's awareness of the event, using the appropriate page of the e-CRF. In case of any eCRF system failure, a paper CRF page may be completed and sent to the sponsor following the same time requirements.

Reporting of adverse events starts from the time point the subject is enrolled in the clinical investigation (i.e., signed informed consent). This means that any adverse events related to or reported during the screening assessments are to be reported.

The principal investigator shall document all adverse events and device deficiencies in the e-CRF that occur any time after informed consent is obtained until 7 days (for non-serious AEs) or 30 days (for SAEs) after the last day of trial participation.

Every SAE will be followed-up until the event is resolved, resolved with sequelae, or until study closure, whichever occurs first.

When required by national or local regulations, the principal investigator shall also notify the EC of all reportable events according to national regulations within the by regulations required timelines and may also be requested by the EC to provide annual reports.

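### Section 9.10 labels as ITT a treated set that omits enrolled subjects excluded for adverse events before implantation, and no denominator is named for ostomy avoidance or complications

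*Combined protocol and SAP*

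**What the plan says.** Section 9.10, headed as the primary analysis population, opens with the rule that "Patients treated with the Colovac 2 Colorectal Anastomosis Protection Device will be included in the intent to treat (ITT) population". Two groups are then set apart:

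- Patients who withdraw consent or prove ineligible before enrollment: the section says that they "will be recorded on a screening log but will not be included in any analyses".
- Enrolled subjects lost before the implant is placed: the section leaves out of the ITT population "Subjects who are enrolled and excluded from the study due to adverse events prior to implantation". For this group it does not say that they are left out of every analysis.

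No other population is defined. Sections 9.7 and 9.8 list ostomy avoidance, device-related complications and all complications as Day 10 endpoints without naming a denominator. The Synopsis and Section 13.0 defer analyses to a SAP, but the combined document contains no separate SAP text.

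The point of enrollment varies. Section 16.1.2 says that "Reporting of adverse events starts from the time point the subject is enrolled in the clinical investigation (i.e., signed informed consent"). Section 10.3 enrolls patients only after consent and an eligibility check, and states that consenting patients who "subsequently do not meet the eligibility criteria will not be included in the intention to treat (ITT) population"; for detail it refers to a section 8.1 that does not exist in the current numbering. Eligibility in Section 10.1 includes intraoperative criteria, one of them open-ended: "Other intra-operative risks that preclude the subject from undergoing the procedure with the investigational device".

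**The concern.** An intent-to-treat set keeps everyone in whom the treatment was intended, whatever happened next. The set in Section 9.10 is conditional on having received the device, and one stated reason for leaving it is an adverse event on the way to receiving it.

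That matters because implantation is part of what is being tested. The investigational device includes the introducer (Synopsis, Section 7.0), its ease of use is a secondary objective (Section 9.6), and Section 14.2 counts the implantation procedure within relatedness to the device. An injury caused by the introducer before the stent is released is a device-related event, yet a subject excluded because of it falls under the last sentence of Section 9.10.

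Eligible patients have a planned diverting ileostomy (Section 10.1), so such a subject would plausibly end with a stoma. Avoiding a stoma is the intended use (Section 8.0). The study has one arm, so no control group is subject to the same selection. At stake is whether the reported ostomy-avoidance rate describes patients in whom the device was tried, or only those in whom it was successfully placed.

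**Working it through.** **Step 1. Trace each kind of subject through Section 9.10.**

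| Subject | Treatment under the text |
|---|---|
| Device implanted | In the ITT set |
| Injured by the introducer before deployment, then excluded | Out, by the last sentence |
| Introducer used, no deployment, no adverse event | Covered by neither rule; depends on the undefined word treated |
| Meets an intraoperative exclusion before the introducer is used | Out of ITT under Section 10.3; whether the no-analyses rule also applies depends on when enrollment occurs |

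The third row is foreseeable: Section 11.2 supplies a back-up device for each procedure, and the use-error notes in Section 14.1 include a user being unable to complete a task.

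**Step 2. Trace the adverse events.** The Synopsis collects them for all subjects, and Section 14.2 does so from consent to the last visit. Section 9.9 covers complications during as well as after surgery. Section 13.0 summarizes all adverse events, including by relationship to device or procedure. Section 14.3 has the events committee assess serious events and adverse device effects. None of these limits itself to the ITT set, and none names a denominator.

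**Step 3. Size for ostomy avoidance.** The plan states no target rate or sample-size calculation, so there is no figure to reproduce. Let N be attempts, k the subjects dropped, x the ostomy-free subjects among those retained, and y the ostomy-free subjects among those dropped.

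- Reported rate: x/(N − k)
- Rate over attempts: (x + y)/N

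The second is a weighted average of x/(N − k) and y/k. The reported rate is therefore too high whenever dropped subjects avoid an ostomy less often than retained ones.

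Assume N = 50, x = 35, y = 0. The rate over attempts is 35/50 = 70.0%.

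- k = 1: 35/49 = 71.4%, up 1.4 points
- k = 2: 35/48 = 72.9%, up 2.9 points
- k = 3: 35/47 = 74.5%, up 4.5 points

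A second set of assumptions holds avoidance among retained subjects near 70%, the randomized-arm rate that Section 4.3 gives for SAFE-2, again with y = 0:

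- k = 1: 34/49 = 69.4% against 34/50 = 68.0%, difference 1.4 points
- k = 3: 33/47 = 70.2% against 33/50 = 66.0%, difference 4.2 points
- k = 5: 31/45 = 68.9% against 31/50 = 62.0%, difference 6.9 points

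**Step 4. Size for device-related complications, only if those rates use the ITT set.** Assume one such event in each dropped subject.

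- k = 1, none among retained: 0/49 = 0% against 1/50 = 2.0%
- k = 3, two among retained: 2/47 = 4.3% against 5/50 = 10.0%

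**Step 5. Compare with sampling error.** The exact two-sided 95% interval for 35/50 is 55.4% to 82.1%. All the ostomy-avoidance rates in Step 3 lie inside it.

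**The case against.** The strongest reply has four parts.

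- **The primary endpoint is untouched.** Migration can occur only once a device is in place, so an implanted-only denominator is right for it. This stands, and the fix keeps it.
- **The last sentence of Section 9.10 is most naturally about surgical events before the device is used**, and leaving those subjects out of a device evaluation is defensible. This stands in part. The wording is not limited to events before introducer insertion, so it also reaches injury by the introducer itself.
- **Other populations may be defined in the SAP.** Possible, but the protocol names only this one, under a heading that makes it primary.
- **The effect is small.** The shifts are a few points, inside a wide interval, for a non-primary endpoint in a preliminary single-arm study with no success threshold. This stands as to severity. However, the interval describes sampling error and does not correct a denominator that loses subjects selectively.

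A reader might infer that harm before deployment could be reported as zero. The documents do not support that. The rule barring subjects from all analyses is applied only to withdrawals and ineligible patients before enrollment, and the provisions in Step 2 of the working leave room for pre-implantation events to be reported outside the ITT set.

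**Conclusion.** The label is wrong, and the stated rule removes a group whose outcome can bear on the device. On a plain reading, a subject excluded because of an introducer injury before deployment leaves the ostomy-avoidance denominator. For complications, the defect is that no denominator is named. The number of subjects affected is unknown: the one to five dropped of 50, the 35 ostomy-free subjects, and the assumption that every dropped subject had an ostomy are all illustrative. On those assumptions the overstatement is about 1 to 7 percentage points. Severity is moderate.

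Three further inferences are tempting and should not be drawn:

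- **That every failed deployment is removed.** The last sentence reaches only exclusions due to adverse events. For a failed attempt without one, the text is silent.
- **That SAFE-2 gives a drop rate of 1 in 27.** Section 4.3 places that event after insertion was completed, with the device then removed surgically. Such a subject would fall inside a treated set.
- **That the sponsor has dropped subjects this way before**, because "partial migration occurred in 4/14 (28.6%) of the first 15 Colovac+ subjects enrolled". Section 4.3 gives no reason for the difference between 14 and 15, and it concerns another study of an earlier device.

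Nor does finishing with fewer than 50 implants contradict the plan, since 50 is stated as a ceiling. What the ceiling counts is simply unclear.

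**What to change.** Revise Section 9.10, and carry the definitions into the SAP before outcomes are known:

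1. Rename the current set the implanted population. Keep it as the denominator for migration, with the number of failed deployments reported beside it.
2. Define an attempted-implant population: every subject in whom introducer insertion is begun, whether or not the implant is deployed. Name it as the denominator for ostomy avoidance and for the device-related and all-complication endpoints.
3. Analyse non-deployed subjects by their actual ostomy status at Day 10, so that no outcome is imputed.
4. List every subject excluded between consent and introducer insertion, with the reason, including those removed under the intraoperative criteria.
5. Use one definition of enrollment in Sections 9.10, 10.3 and 16.1.2, correct the reference to section 8.1, and state whether the 50 counts enrolled, attempted or implanted subjects.

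The cost is about a paragraph of text plus the cross-reference corrections. Adverse events and ostomy status are already collected; the one check needed is that the surgery form records whether introducer insertion was begun. The reported rates may be slightly less favourable.
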